5.1 Imputation rules

5.1.1 Study drug

The following rule should be used for the imputation of the dose end date for a given study treatment component:

Scenario 1: If the dose end date is completely missing and there is no EOT page and no death date, the patient is considered as on-going:

The patient should be treated as on-going and the cut-off date should be used as the dose end date.

Scenario 1 should not applicable for final CSR. All patients should have EOT page complete before the Database lock for Final CSR

Scenario 2: If the dose end date is completely or partially missing and the EOT page is available:

Case 1: The dose end date is completely missing, and the EOT completion date is complete, then this latter date should be used.

Case 2: Only Year(yyyy) of the dose end date is available and yyyy < the year of EOT date:

- **Use Dec31yyyy**

Case 3: Only Year(yyyy) of the dose end date is available and yyyy = the year of EOT date:

- **Use EOT date**

Case 4: Both Year(yyyy) and Month (mm) are available for dose end date, and yyyy = the year of EOT date and mm < the month of EOT date:

- **Use last day of the Month (mm)**

All other cases should be considered as a data issue and the statistician should contact the data manager of the study.

After imputation, compare the imputed date with start date of treatment, if the imputed date is start date of treatment:

- **Use the treatment start date**

Patients with missing start dates are to be considered missing for all study treatment component related calculations and no imputation will be made. If start date is missing then end-date should not be imputed.

5.1.2 AE, ConMeds and safety assessment date imputation

Table 5-1 Imputation of start dates (AE, CM) and assessments (LB, EG, VS)

Missing Element	Rule
day, month, and year	
 • No imputation will be done for completely missing dates
day, month	
 • If available year = year of study treatment start date then 
 ○ If stop date contains a full date and stop date is earlier than study treatment start date then set start date = 01JanYYYY ○ Else set start date = study treatment start date. • If available year > year of study treatment start date then 01JanYYYY • If available year < year of study treatment start date then 01JulYYYY

Missing Element	Rule
day	
• If available month and year = month and year of study treatment start date then
○ If stop date contains a full date and stop date is earlier than study treatment start date then set start date= 01MONYYYY.○ Else set start date = study treatment start date.• If available month and year > month and year of study treatment start date then 01MONYYYY• If available month and year < month year of study treatment start date then 15MONYYYY

Table 5-2 Imputation of end dates (AE, CM)

Missing Element	Rule (* = last treatment date plus 30 days not > (death date, cut-off date, withdrawal of consent date))
day, month, and year	• Completely missing end dates (incl. ongoing events) will be imputed by the end date of the on-treatment period*
day, month	• If partial end date contains year only, set end date = earliest of 31DecYYYY or end date of the on-treatment period *
day	• If partial end date contains month and year, set end date = earliest of last day of the month or end date of the on-treatment period*

Any AEs and ConMeds with partial/missing dates will be displayed as such in the data listings.

Any AEs and ConMeds which are continuing as per data cut-off will be shown as 'ongoing' rather than the end date provided.

The above imputations are only used for analyses of time to and duration of AEs and concomitant medications.

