2.1 Data analysis general information

All analysis will be performed by Novartis and/or a designated CRO. SAS version 9.4 or later software will be used to perform all data analyses and to generate tables, figures and listings. Analysis using Rshiny apps might also be used as needed.

Data included in the analysis

The analysis cut-off date for the primary analysis of study data will be established after all randomized patients in the expansion arm have either completed nine months of follow-up or have discontinued study. For the selection phase, interim analyses will be conducted once the 1st 10 subjects have been enrolled in each of the 1st three arms and then conducted approximately every 20 weeks thereafter. No formal interim analysis for efficacy will be conducted for combination arms in the expansion phase.

For each of the analyses, all statistical analyses will be performed using all data collected in the database up to the data cut-off date. All data with an assessment date or event start date (e.g. vital sign assessment date or start date of an adverse event) prior to or on the cut-off date will be included in the analysis. Any data collected beyond the cut-off date will not be included in the analysis and will not be used for any derivations.

All events with start date before or on the cut-off date and end date after the cut-off date will be reported as 'ongoing'. The same rule will be applied to events starting before or on the cut-off date and not having documented end date. This approach applies, in particular, to adverse event and concomitant medication reports. For these cases, the end date will not be imputed and therefore will not appear in the listings.

The analysis cutoff date for the final analysis of study data will be established at the end of the study defined as the earliest occurrence of one of the following:

- All subjects have died or discontinued from the study
- Another clinical study (i.e. rollover study) becomes available that can continue to provide the appropriate combination treatment in this subject population and all subjects ongoing are eligible to be transferred to that clinical study

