Table 2-7	Categories of anti-neoplastic therapies since discontinuation
Category	Sub-category
Immunotherapy	Anti-CTLA-4
	Anti-PD-1/Anti-PD-L1
	Combination Anti-CTLA-4 + Anti-PD-1/Anti-PD-L1
	IL-2
	Interferon
	Other or investigational
Targeted therapy	
Chemotherapy	
Radiotherapy	
Surgery	
Other or investigational	

Concomitant medications

Concomitant therapy is defined as all interventions (therapeutic treatments and procedures) other than the study treatment administered to a patient coinciding with the study treatment period. Concomitant therapy include medications (other than study drugs) starting on or after the start date of study treatment or medications starting prior to the start date of study treatment and continuing after the start date of study treatment.

Concomitant medications will be coded using the World Health Organization (WHO) Drug Reference Listing (DRL) dictionary that employs the WHO Anatomical Therapeutic Chemical (ATC) classification system and summarized by lowest ATC class and preferred term using

frequency counts and percentages. Surgical and medical procedures will be coded using MedDRA and summarized by SOC and preferred term. Concomitant medications with immunosuppressive intent will be summarized by lowest ATC class and preferred term using frequency counts and percentages.

All reported systemic steroids will be summarized by lowest ATC class and preferred term using frequency counts and percentages. Reported cumulative dose and maximum cumulative dose, adjusted for relative anti-inflammatory potency [Schimmer and Parker 1996], will also be summarized along with route of administration.

Table 2-8 Systemic steroid anti-inflammatory potency relative to Hydrocortisone

Steroid Name	Anti-inflammatory potency, relative to Hydrocortisone
Hydrocortisone	1
Cortisone acetate	0.8
Prednisone	4
Prednisolone	4
Methylprednisolone	5
Dexamethasone	30

All summaries will include:

1. Medications starting on or after the start of study treatment but no later than 30 days after last dose of study treatment and
2. Medications starting prior to start of study treatment and continuing after the start of study treatment.

Additional summaries will be provided to report medications starting between 31 days after last dose of study treatment and 150 days after last dose of PDR001.

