2.8.1.1 Adverse events of special interest / grouping of AEs

Adverse events of special interest (AESI) during the on-treatment period will be tabulated. The list of AESI will also include relevant events for spartalizumab, and the novel agents.

Data analysis of AESIs

An adverse event of special interest (AESI) is a grouping of adverse events that are of scientific and medical concern specific to compound PDR001, the individual novel agents, as well as combination specific AESIs (PDR001 + novel agent). These groupings are defined using MedDRA terms, SMQs (standardized MedDRA queries), HGLTs (high level group terms), HLT (high level terms) and PTs (preferred terms). Customized SMQs (Novartis MedDRA queries, NMQ) may also be used. A NMQ is a customized group of search terms which defines a medical concept for which there is no official SMQ available or the available SMQ does not completely fit the need. It may include a combination of single terms and/or an existing SMQ, narrow or broad. All AESI terms for the individual compounds as well as for combination specific AESIs are captured in the case retrieval strategy (CRS).

For each specified AESI, number and percentage of patients with at least one event of the AESI occurring during on treatment period will be summarized.

Summaries of these AESIs will be provided by treatment arm, (specifying grade, SAE, relationship, leading to treatment discontinuation, leading to dose adjustment/interruption, hospitalization, death, requiring immunosuppressive medication etc.). If sufficient number of events occurred, analysis of time to first occurrence will be applied.

Additional summaries will be provided to report all AESIs, AESIs related to study treatment, all serious AESIs and serious AESIs related to study treatment collected during the on-treatment period and up to 150 days after last administration of PDR001.

A listing of all grouping levels down to the MedDRA preferred terms used to define each AESI will be generated. This listing should be included in section 16 of CSR.

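### Table 5-2 can end AEs and medications without a complete end date before they start, because it caps their end at last treatment + 30 days with no check against the start date

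*SAP*

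**What the plan says.** Table 5-2 in Section 5.1.2 of the main SAP gives the end-date rules for AEs and concomitant medications:

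- No end date at all: "Completely missing end dates (incl. ongoing events) will be imputed by the end date of the on-treatment period".
- Month and year known: "set end date = earliest of last day of the month or end date of the on-treatment period". The year-only rule has the same form, with 31 December in place of the month end.
- The footnote defines the cap: "last treatment date plus 30 days not > (death date, cut-off date, withdrawal of consent date").

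The text below the table limits the use of these dates: "The above imputations are only used for analyses of time to and duration of AEs and concomitant medications". It also fixes how they are displayed: "Any AEs and ConMeds which are continuing as per data cut-off will be shown as 'ongoing' rather than the end date provided".

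Elsewhere the SAP reports events beyond day 30. Section 2.8.1.1 adds summaries of AESIs "collected during the on-treatment period and up to 150 days after last administration of PDR001"; Sections 2.1.1 and 2.8.1 do the same for AEs and SAEs. Section 2.4.2 adds summaries of "medications starting between 31 days after last dose of study treatment and 150 days after last dose of PDR001".

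Section 2.1, on events that run past the cut-off or have no documented end, says: "For these cases, the end date will not be imputed and therefore will not appear in the listings".

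The Arm 1A SAP (Sections 5.1.2 and 5.1.3) takes over the AE and medication imputation rules of the main SAP.

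**The concern.** The cap belongs to the on-treatment period, but the table is not limited to events that start in that period. Three things follow for a patient who has stopped treatment:

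- An event that starts after the cap and has no complete end date is given an end before its start.
- A partial end date that is known to lie in a later month is moved back to day 30, although the same event with a complete end date would keep it.
- An event that began on treatment and has not resolved is treated as finished at day 30, so a censored duration becomes a completed one.

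All three errors shorten durations, and they fall on late-onset and non-resolving events. Section 5.1.1 compares an imputed dose end date with the treatment start date; Table 5-2 has no such check. A programmer who meets a negative duration has to improvise, and may do so differently from one analysis to the next.

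**Working it through.** The plan gives no figure to reproduce, so the check applies Table 5-2 as written.

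**Inputs.** Cap = last study treatment + 30 days (Table 5-2 footnote). Post-treatment period from day 31 (Section 2.1.1). Reporting window to day 150 after the last PDR001 dose (Sections 2.1.1, 2.8.1, 2.8.1.1). Two illustrative dates: last dose 28-Jul-2019, an example date in Section 2.1.1, and an assumed cut-off of 30-Jun-2020, which is 338 days later. No earlier death or consent withdrawal.

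**Ongoing events.** With s = start day counted from the last dose, duration = end - start + 1. Under Table 5-2 this is 30 - s + 1. If the event is followed to day 150 it is at least 150 - s + 1, and to the assumed cut-off at least 338 - s + 1.

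| Start day s | Table 5-2 | To day 150 | To cut-off |
|---|---|---|---|
| -60 | 91 | 211 | 399 |
| 20 | 11 | 131 | 319 |
| 31 | 0 | 120 | 308 |
| 60 | -29 | 91 | 279 |
| 100 | -69 | 51 | 239 |
| 150 | -119 | 1 | 189 |

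The imputed end precedes the start whenever s > 30, which is all 150 - 30 = 120 start days from 31 to 150 when every component stops on the same day.

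**Partial end dates.** The cap date is 28-Jul-2019 + 30 = 27-Aug-2019.

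- Start on day 60 (26-Sep-2019), end recorded as October 2019: the earlier of 31-Oct-2019 and 27-Aug-2019 is 27-Aug-2019, so the duration is 30 - 60 + 1 = -29 days. The month end would give 5 + 31 = 36 days.
- Start on day 20 (17-Aug-2019), end recorded as October 2019: Table 5-2 gives 30 - 20 + 1 = 11 days. The recorded month alone bounds the true value between 15 + 30 + 1 = 46 days (1 October) and 15 + 30 + 31 = 76 days (31 October).

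**Partner drug continued.** Table 5-2 counts from the last dose of any study treatment, whereas the AE window counts from the last PDR001 dose. If the partner runs x days longer, the cap lies at day 30 + x after PDR001, and 150 - (30 + x) = 120 - x start days are reversed: 90 for x = 30, 60 for x = 60, none for x = 120. The separate medication window in Section 2.4.2 opens 31 days after the last study treatment, so every medication in it without a complete end date is reversed, whatever x is.

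**Patients still on treatment.** If the last Q4W infusion was 28 days or less before the cut-off, last dose + 30 exceeds the cut-off, and the end is set to the cut-off. Here the rule gives the duration observed so far.

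**The case against.** The strongest objection is that no output named in the SAP uses these end dates. Section 5.1.2 confines them to time-to and duration analyses. The one time-to AE analysis named, first occurrence of an AESI (Section 2.8.1.1), depends on start dates, and the Arm 1A SAP drops it. Section 2.8 says that duration will be recorded, but no duration table is specified. The day 31 to 150 summaries count events and medications by start. All of this stands, and it limits the weight.

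Four stronger readings are tempting, and the documents do not support them:

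- A reader might infer that every event in the extended window ends before it starts. Complete end dates are kept, patients still on treatment generally end at the cut-off, and a continuing partner drug shrinks the affected AE range.
- A reader might infer that the 150-day safety picture is distorted. Incidence counts and listings do not change.
- A reader might infer that cumulative steroid dose is truncated. Section 2.4.2 refers to reported dose, and nothing derives it from imputed dates.
- A reader might infer a flat contradiction with Section 2.1. That text can be read as a display rule, consistent with showing events as ongoing in Section 5.1.2. Its wording is broader than that, so it needs a cross-reference.

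It is also fair to say that stopping the clock at day 30 is a coherent choice if the target is duration within the on-treatment period. The SAP does not state that target, and the rule is not limited to events that start on treatment.

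None of this answers the core point: for the one use where imputed end dates matter, duration, the rule yields impossible or falsely short values.

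**Conclusion.** The rule is wrong as written, at minor-to-moderate weight. For patients off treatment, an AE or medication without a complete end date that starts more than 30 days after the last study treatment, but within the 150-day post-PDR001 window, gets a duration of 0 to -119 days. That range assumes that all components stop together and that no death, cut-off or consent withdrawal comes earlier. Unresolved on-treatment events, and events with a known later end month, are cut at day 30. The number of events affected cannot be estimated from the documents. The consequence is confined to duration analyses of AEs and medications.

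**What to change.** In Table 5-2 of the main SAP:

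- For partial end dates, remove the cap at the end of the on-treatment period. Use the last day of the known month, or 31 December of the known year, not later than death, cut-off or consent withdrawal.
- Require that an imputed end date is never earlier than the start date.
- In any duration summary, treat ongoing events as censored at the earliest of cut-off, death, consent withdrawal or end of AE collection, rather than as ended at day 30. If an on-treatment duration is what is wanted, label it so and restrict it to events that start on treatment.
- Cross-reference Section 2.1, so that its statement on not imputing end dates is reconciled with Table 5-2.

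Apply the same text to Arm 1A through Sections 5.1.2 and 5.1.3 of its SAP. The cost is a change of wording and a small programming change; no new data are needed.

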5.1.2.1 Other imputations

Incomplete date of initial diagnosis of cancer and date of most recent recurrence

Missing day is defaulted to the 15th of the month and missing month and day is defaulted to 01-Jan.

Incomplete assessment dates for tumor assessment

All investigation dates (e.g. MRI scan, CT scan) must be completed with day, month and year. If one or more assessment dates are incomplete but other investigation dates are available, this/these incomplete date(s) are not considered for calculation of the assessment date and assessment date is calculated as the latest of all investigation dates (e.g. MRI scan, CT scan) if the overall response at that assessment is CR/PR/SD/UNK. Otherwise – if overall response is progression – the assessment date is calculated as the earliest date of all investigation dates at that evaluation number. If all measurement dates have no day recorded, the 1st of the month is used. If the month is not completed, for any of the investigations, the respective assessment will be considered to be at the date which is exactly between previous and following assessment. If a previous and following assessment is not available, this assessment will not be used for any calculation.

Applying the cut-off to tumor assessment

For tumor related assessments, if an evaluation has some assessments done prior to cut-off date and others after the cut-off date, then the evaluation is considered post-cut-off date and will be excluded from analysis.

5.2 AEs coding/grading

Adverse events are coded using the Medical dictionary for regulatory activities (MedDRA) terminology.

Note: The latest available MedDRA version at the time of the analyses should be used. The MedDRA version used should be specified in the footnote of relevant tables.

AEs will be assessed according to the Common Terminology Criteria for Adverse Events (CTCAE) version 4.03.

The CTCAE represents a comprehensive grading system for reporting the acute and late effects of cancer treatments. CTCAE grading is by definition a 5-point scale generally corresponding to mild, moderate, severe, life threatening, and death. This grading system inherently places a value on the importance of an event; although there is not necessarily proportionality among grades (a grade 2 is not necessarily twice as bad as a grade 1).

5.3 Laboratory parameters derivations

Grade categorization of lab values will be assigned programmatically as per NCI Common Terminology Criteria for Adverse Events (CTCAE) version 4.03. The calculation of CTCAE grades will be based on the observed laboratory values only, clinical assessments will not be taken into account. The criteria to assign CTCAE grades are given in Novartis internal criteria for CTCAE grading of laboratory parameters. The latest available version of the document based on the underlying CTCAE version 4.03 at the time of analysis will be used. The Novartis internal CTC grading document should be added as appendix to the SAP and to Section 16.1.9 of the CSR. For laboratory tests where grades are not defined by CTCAE version 4.03, results will be graded by the low/normal/high (or other project-specific ranges, if more suitable) classifications based on laboratory normal ranges.

A severity grade of 0 will be assigned for all non-missing lab values not graded as 1 or higher. Grade 5 will not be used. For laboratory tests that are graded for both low and high values, summaries will be done separately and labelled by direction, e.g., sodium will be summarized as hyponatremia and hypernatremia.

Imputation Rules

Common Toxicity Criteria (CTC) grading for blood differentials is based on absolute values. However, this data may not be reported as absolute counts but rather as percentage of WBC.

If laboratory values are provided as '<X' (i.e. below limit of detection) or '>X', prior to conversion of laboratory values to SI unit, these numeric values are set to X.

The following rules will be applied to derive the WBC differential counts when only percentages are available for an xxx differential

$$xxx\ count = (WBC\ count) * \left(\frac{xxx\ \% \ value}{100} \right)$$

Further derivation of laboratory parameters might be required for CTCAE grading. For instance, corrected calcium can be derived using the reported total calcium value and albumin at the same assessment using the following formula:

$$\text{Corrected Calcium } \left(\frac{\text{mg}}{\text{dL}}\right) = \text{Calcium } \left(\frac{\text{mg}}{\text{dl}}\right) - 0.8 \left[\text{Albumin } \left(\frac{\text{g}}{\text{dL}}\right) - 4 \right]$$

In order to apply the above formula, albumin values in g/L will be converted to g/dL by multiplying by 0.1), calcium values in mmol/L will be converted to mg/dL by dividing by 0.2495. For calculation of laboratory CTC grades 0 and 1, the normal range for derived corrected calcium is set to the same limits (in mg/dL) as for calcium.

CTC grades for the derived absolute WBC differential counts (neutrophils, lymphocytes) and corrected calcium will be assigned as described above for grading

5.4 Statistical models

5.4.1 Primary analysis

Please refer to Section 10 of the protocol, [Section 2.5.2](#), and the [\[SAP Technical Appendix\]](#) for extended details on the modeling and SAS procedures used for both the selection and expansion phases of the trial. Other details for the primary analysis are shown below

Analysis of Binary Data

Single arm study

For the selection phase, the following statistical hypothesis will be tested:

$$H_0: \text{ORR} \leq 10 \% \text{ will be tested vs } H_1: \text{ORR} > 10 \%$$

using a one-sided test with $\alpha=0.025$ based on the exact binomial distribution.

Responses will be summarized in terms of percentage rates with 95% CIs. An exact binomial confidence interval (implemented using SAS procedure FREQ with EXACT statement for one-way tables) will be calculated [\[Clopper and Pearson 1934\]](#)

SAS procedure FREQ will be used to estimate the proportion of responders (binary outcome = 1 or “Yes”), along with the associated 95% ($=100 \times (1 - \text{two-sided alpha level})$) two-sided Pearson-Clopper CI and exact one-sided p-value for the hypothesis test of the *null proportion* (0.10).

Confidence interval for response rate

Responses will be summarized in terms of percentage rates with $100(1 - \alpha)\%$ confidence interval using exact binomial confidence interval (implemented using SAS procedure FREQ with EXACT statement for one-way table [\[Clopper and Pearson 1934\]](#)).

